3 SUBJECT SELECTION AND WITHDRAWAL

A total of 20 participants will be recruited for this study and all data will be collected at UNC-CH. No specific plans have been made to enroll participants from vulnerable populations.

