5.1.2 INITIAL SCREENING SESSION (VISIT 1)

At day 1 of stimulation, participants will be guided through the consent form and the HIPAA authorization form and be given the time to ask any questions about the information discussed. To ensure that all aspects of the research are understood, participants may be asked a series of questions about the research they are about to take part in (*Appendix E*). Once it is clear that the participant understands the consent form and HIPAA authorization, they may sign the forms.

Following the consent process, the participant completes the ODI and DVPRS to measure disability and pain intensity on 0-11 scale. The HAM-D and DASS-21 will assess low suicide risk and depression level. The self-report measures: UCLA Activity Score, PCS, and PSEQ will assess physical activity limitations, pain experience, and confidence in daily activities. Data on demographics, handedness, stai, bis-bas, and opinion pre-treatment will also be collected.

Once eligibility has been confirmed and all relevant data collected, Day 1 of stimulation will begin.

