5.2.2 DAYS 2 OF STIMULATION (VISIT 2)

Prior to starting any study procedures, female participants will be asked to take a urine pregnancy test to ensure continued eligibility. The ODI, DVPRS, 5xSST, FTF, and pressure pain threshold test will be administered before stimulation. A resting state EEG will be recorded for 5 min before and after stimulation. The participant will receive 40 minutes of sham or 10 Hz tACS stimulation (as per the initial randomization) while watching “Reefscape”. The stimulation will be followed by the pressure pain threshold, 5xSST, FTF, stimulation adverse effects questionnaire and perceived improvement ending the session.

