5.3 FOLLOW-UP

5.3.1 FOLLOW-UP EMAIL

Two days after both sessions of stimulation, participants will receive an email with a follow up survey to assess any change in pain perception. The ODI and DVPRS will take approximately 15 minutes to complete.

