6.3 SPECIAL ASSAYS OR PROCEDURES

6.3.1 SPECIAL PROCEDURES

Each participant will attend two days of stimulation for this study. Each participant will be randomly assigned to one of two treatment arms (sham or 10 Hz tACS) then the opposite on the second visit. For more information on the stimulation procedures, see section 7.2 *Preparation and Administration of Study Investigational Product*.

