11 STATISTICAL PLAN

11.1 STATISTICAL ANALYSIS STRATEGIES

Our study design is a AB/BA crossover and we will ensure a washout effect by scheduling 1-3 weeks between stimulation sessions. A continuous outcome approach will be used to analyze the crossover trial data where carryover effects will be assumed to be equal.

Primary outcome: Use kubios software to analyze HRV over before and after stimulation. A standard spectral analysis will be applied to the pre and post intervals, including total power, HF, LF, and HP. Specifically looking at the HF component since it reflects the parasympathetic modulation of the heart rate. Use a repeated measure ANOVA with factor session (1 vs 2) and factor treatment (active vs sham) (R software). We hypothesize a treatment main effect and with no session effect and no interaction.

Secondary outcome: A Mann-Whitney-Wilcoxon rank-sum testMann Whitney U test (R software) will be performed on the self-report VAS pain scale (nonparametric scale) (from DVPRS) before and after stimulation as well as between sessions to analyze any differences in self-report perceived pain. Grouped ANOVAs and unpaired t-tests may also be used to analyze correlations within other self-report measures

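### Grouped ANOVAs and unpaired t-tests do not fit the other self-report measures: they discard the pairing if used for active versus sham on scales taken under both conditions, and they estimate no correlation

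*Combined protocol and SAP*

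**What the plan says.** Section 11.1 states the design: "Our study design is a AB/BA crossover and we will ensure a washout effect by scheduling 1-3 weeks between stimulation sessions". Section 6.3.1 confirms that both conditions occur in the same person: "Each participant will be randomly assigned to one of two treatment arms (sham or 10 Hz tACS) then the opposite on the second visit". Section 3 sets the number: "A total of 20 participants will be recruited for this study".

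For the primary HRV outcome, Section 11.1 chooses a within-subject method with session and treatment as factors: "Use a repeated measure ANOVA with factor session (1 vs 2) and factor treatment (active vs sham". The DVPRS pain rating then has its own rank test, which is outside this point. For everything else that participants report, the plan offers one sentence: "Grouped ANOVAs and unpaired t-tests may also be used to analyze correlations within other self-report measures". It names no scale, contrast or correlation coefficient, and does not define a grouped ANOVA. No other section gives a method for these measures.

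The visit descriptions show which scales recur:

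- **Under both conditions.** The ODI and DVPRS are completed at visit 1 before stimulation (5.1.2) and again at visit 2 (5.2.2: "The ODI, DVPRS, 5xSST, FTF, and pressure pain threshold test will be administered before stimulation"). Both also form the email survey after each session (5.3.1: "The ODI and DVPRS will take approximately 15 minutes to complete"). Perceived improvement closes each session (5.2.1, 5.2.2). The DVPRS has supplementary questions on daily living (6.1).
- **At visit 1 only.** Section 5.1.2 says: "The self-report measures: UCLA Activity Score, PCS, and PSEQ will assess physical activity limitations, pain experience, and confidence in daily activities". The same section places the DASS-21, STAI and BIS-BAS there. No later visit description mentions any of these six.

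**The concern.** There are two separate problems.

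First, an unpaired t-test or between-group ANOVA of active against sham values on a recurring scale would treat 20 people measured twice as 40 independent people. Its standard error would include between-person variation, which the crossover was chosen to remove. The primary analysis in the same section does respect the repeated structure.

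Second, the stated purpose is correlation. A t-test or ANOVA compares means. Neither estimates how strongly two scale scores are associated, so the sentence does not say how its own aim would be met.

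Section 11.2 says the results will inform the sample sizes of later trials. An unpaired analysis would report intervals that are too wide for the recurring scales, and would not yield the within-person SD that planning another crossover needs.

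**Working it through.** The plan has no power or sample-size figure to reproduce: Section 11.2 says none was calculated. What follows is an illustration.

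**From the documents:** 20 participants, hence n = 20 active/sham pairs if all complete; both conditions in each person.

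**Assumed, because the documents give no values for these scales:** two-sided 5% test; normal data with equal SD (sigma) under both conditions; no period or carryover effect; true difference d = 0.5 sigma; rho = 0.3, 0.5 or 0.7.

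**Step 1, standard errors of the active-minus-sham mean.**

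- Assumed by the unpaired test: sigma × sqrt(2/n) = sigma × sqrt(2/20) = 0.316 sigma.
- Correct for pairs: sigma × sqrt(2(1-rho)/n) = 0.265, 0.224 and 0.173 sigma at rho = 0.3, 0.5 and 0.7.
- Ratio: 1/sqrt(1-rho) = 1.20, 1.41 and 1.83.

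**Step 2, error rate and power.** Simulation with 100,000 replicates. The AB/BA column is a two-sample t-test of within-participant period differences, 10 people per sequence.

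| rho | True type I error, unpaired | Power, unpaired | Power, paired | Power, AB/BA |
|---|---|---|---|---|
| 0.3 | 2.1% | 31% | 43% | 43% |
| 0.5 | 0.8% | 28% | 57% | 56% |
| 0.7 | 0.1% | 24% | 78% | 78% |

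The paired and AB/BA tests held their type I error at 5.0% to 5.1%. The noncentral t distribution gives paired power of 43.4%, 56.5% and 78.2%, in agreement with the simulation.

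**Step 3, sensitivity.** At rho = 0 the two tests are about equal (34% unpaired, 32% paired). At d = 0.8 the gap is smaller at the two higher correlations: 72%, 76% and 80% unpaired against 82%, 92% and 99% paired.

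**Step 4, where this applies.** It needs an active and a sham value from the same person. The ODI, the DVPRS supplementary items and perceived improvement have these. The UCLA, PCS, PSEQ, DASS-21, STAI and BIS-BAS, as described, do not.

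**The case against.** The sentence is permissive and sits at the lowest tier of a pilot. The primary objective rests on HRV and the secondary on perceived pain (2.4.1), so neither depends on it. Nor does it say that active will be compared with sham. Some uses of an unpaired test would be sound. Comparing period differences between the AB and BA sequences is a standard crossover analysis and, as the table shows, costs almost no power. Comparing true between-person groups is also legitimate, and Section 6.5.2 plans exploratory grouping by BDNF status.

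Much of this stands. A reader might infer that every other self-report scale loses its pairing. The visit descriptions do not support that, since six scales are described only at visit 1. A reader might infer that the plan commits itself to analysing 40 values as independent. It does not: the contrast is left open. A reader might also fear inflated false positives, but with positive correlation the error runs the other way, and the estimated mean difference does not change when pairs are complete.

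Two things remain. Section 11.1 does not tie the tests to either sound use, and it offers no other method for these measures. And no choice of contrast makes a t-test or ANOVA an estimate of correlation.

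**Conclusion.** The point holds in a limited form and is minor. The mismatch between the tests and their stated purpose is certain from the text and covers all the other self-report measures. The loss of pairing is conditional: it arises only if the tests are used for active against sham, and only on measures taken under both conditions. There the standard error would be about 1.2 to 1.8 times too large for rho of 0.3 to 0.7, with the power loss shown above.

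Those figures depend on the assumed d and rho, on 20 complete pairs and on normal data. The direction is secure for any positive rho; the exact percentages are not. The documents do not support a conclusion that pilot signals will be missed: that would also need a decision by significance test, and no such rule is stated for these scales. The primary HRV analysis is not touched.

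**What to change.** Replace the sentence in Section 11.1 with three statements:

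1. Each self-report measure taken under both conditions is analysed with the within-participant crossover model already chosen for the primary outcome (participant, session, treatment). With complete data, a two-sample test of within-participant period differences between the AB and BA sequences is equivalent; a rank-based version suits an ordinal item such as perceived improvement. Name the measures and the contrast, for example the ODI after active against the ODI after sham. A plain paired t-test is second best, because it ignores the session factor that the plan itself includes.
2. Where association between scales is the question, report the Spearman correlation with a confidence interval and name the pairs of measures.
3. Unpaired t-tests and between-group ANOVAs are kept for true between-person groups, such as BDNF status.

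The cost is a rewrite of one sentence. It needs no new data, visits or participants.

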11.2 SAMPLE SIZE DETERMINATION

This clinical trial represents a pilot study. A pilot study is a clinical trial that is conducted to decide whether a new treatment should be tested in a large controlled trial; therefore, we do not calculate sample size. This study can be considered a pilot study, as it is the first time this specific treatment will be performed on this clinical population. The results from this study will be used to determine sample sizes for future, large-scale clinical trials. In addition, we have to restrict the number of included participants to a small sample size due to limited funding resources.

11.3 DATA MANAGEMENT

Data will be stored in a password-protected cloud-based data system that does not contain any patient information. Individual records are referred to by dummy identifiers that cannot be traced back to the study participants except with the master code list that is stored separately in a secured location.

12 DATA HANDLING AND RECORD KEEPING

The study coordinator and research assistants are responsible for the accuracy, completeness, legibility, and timeliness of the data reported.

12.1 PHI AND HIPAA

Information about study participants will be kept confidential and managed according to the requirements of the Health Insurance Portability and Accountability Act of 1996 (HIPAA). Those regulations require a signed subject authorization informing the subject of the following:

- What protected health information (PHI) will be collected from the participants in this study
- Who will have access to that information and why
- Who will use or disclose that information
- The rights of a research subject to revoke their authorization for use of their PHI.

In the event that a participant revokes authorization to collect or use PHI, the investigator, by regulation, retains the ability to use all information collected prior to the revocation of participant authorization. For participants that have revoked authorization to collect or use PHI, attempts should be made to obtain permission to collect at least vital status (i.e., that the subject is alive) at the end of their scheduled study period.

12.2 CONFIDENTIALITY

To ensure confidentiality, all data will only be referenced by a dummy identifier. Source documents (i.e. paper forms) will be kept in a locked file cabinet in a locked office. In addition, all data will be stored on a password-protected computer using a password-protected data collection tool (REDCap). The key linking dummy identifiers with participant information will be securely located separate from all other data collected.

12.2.1 ACCESS TO SOURCE DOCUMENTS

The research coordinator, research assistants, and PI will have access to all of the source documents collected over the course of the study. The Co-I and medical monitor will have access to files upon request, as they will need access to the locked rooms and filing cabinets in which these documents are located.

Data will stay on a password-protected computer. Subsequently, a copy will be processed on a separate, password-protected desktop computer in the [name] Lab ([name]).

12.2.2 SENSITIVE INFORMATION

Sensitive information will be collected in this study, including information about medical conditions and drug use. We are using the DASS-21 and HAM-D to assess comorbid depression and ensure that the participant meets eligibility criteria (low suicide risk).

12.2.3 OTHER

Please note that there is no significant risk of deductive disclosure in this study. In addition, none of the groupings or subgroupings used in analysis will be small enough to allow individuals to be identified.

12.3 SOURCE DOCUMENTS

Source data is all information, original records of clinical findings, observations, or other activities in a clinical trial necessary for the reconstruction and evaluation of the trial. Source data are contained in source documents. Source data include:

PARTNERS HUMAN RESEARCH COMMITTEE (IRB).

- All IRB correspondences are documented
- The study staff is IRB approved prior to performing any study procedures
- Adverse events and deviations are reported to the IRB per current guidelines and stored appropriately
- All versions of the IRB protocols and informed consent forms are on file

INFORMED CONSENT.

- Ensure that participant identification is not recorded on the ICF (i.e., no participant ID)
- There is documentation that the participant is given a copy of the consent form
- The participant and study representative signed and dated the consent form for him/herself
- The participant initialed and dated all appropriate pages on the informed consent form
- Note to file (Appendix F) made for any informed consent deviations
- Ensure a valid (current version date) copy of the consent form was used

PROTOCOL DEVIATIONS.

- Any and all protocol deviations (exceptions and violations) are documented in the participant folder and reported to the IRB as required

OTHER SOURCE DOCUMENTS.

- Each participant folder will contain a checklist to ensure that all source documents are administered and collected properly. The checklist will be dated by the researcher for each time an assessment is administered
- Review participant folders to ensure the accuracy, completeness, and legibility of the data.
- Any correction made to the source documents is dated, initialed, and explained. The original entry should not be obscured.
- The protocol-specific source documents are on file.
- Source documents are completed in ink.
- Note to files (Appendix F) are made for missing or incomplete data and to explain any discrepancies or additional comments.

DNA.

- Participant names will not be on any of the samples collected. DNA is sequenced to check for one nucleotide. When testing is performed, only de-identified information is shared with an outside party. This information will not be shared with anyone outside of the study personnel, including the participant.

12.4 DATA MANAGEMENT RESPONSIBILITIES

The responsibilities designated to each member of the research team are documented on the Delegation of Authority Form. The study coordinator and research assistants will be responsible for the informed consent process, review for eligibility, questionnaire administration, data entry, device administration, and EKG administration. The study coordinator will be responsible for AE/SAE documentation and reporting, while the PI will be responsible for the AE assessment, review of the AE documentation forms, and overview of the research staff. [name] will be the medical monitor for the study.

REDCap will serve as a secure data management tool for this study. The study coordinator and research assistants will have complete access to the REDCap system, while the PI and Co-I will have read-only ability. This will enable to researchers to enter the data and the PI and Co-I to review.

12.5 DATA CAPTURE METHODS (REDCAP)

Clinical data (including AEs, concomitant medications, and expected adverse reactions data) and clinical laboratory data will be entered into a data capture system provided by REDCap. The data system includes password protection and internal quality checks, such as automatic range checks, to identify data that appear inconsistent, incomplete, or inaccurate. Clinical data will be entered directly from the source documents.

All assessments completed by the participant at home will be completed via REDCap as well, ensuring participant security and confidentiality.

12.6 PROTOCOL DEVIATIONS

All deviations from the protocol will be addressed in study participant source documents. The researcher will complete a Protocol Deviation Log using the participant code as the identifier. This form will collect information such as the date the deviation occurred, details of what the deviation consisted of, any corrective and preventative actions that were taken as a result of the deviation, and the date that the PI and IRB were notified. The PI will review the information and initial once approved. A completed copy of the Protocol Deviation Form will be maintained in the regulatory file, as well as in the participant's source document. Protocol deviations will be sent to the IRB per their guidelines. The site PI/study staff will be responsible for knowing and adhering to their IRB requirements.

12.7 RECORD RETENTION

According to the University of North Carolina at Chapel Hill's Archives and Record Management Services schedule for General Records Retention and Disposition Schedule 6.10, records will be kept for 5 years after the completion of the study or grant end date, whichever is later.

13 ETHICAL CONSIDERATIONS

13.1 ETHICAL STANDARD

The investigator will ensure that this study is conducted in full conformity with the principles set forth in the Belmont Report: Ethical Principles and Guidelines for the Protection of Human Subjects of Research, as drafted by the US National Commission for the Protection of Human Subjects of Biomedical and Behavioral Research (April 18, 1979) and codified in 45 CFR Part 46 and/or the ICH E6; 62 Federal Regulations 25691 (1997).

13.2 INSTITUTIONAL REVIEW BOARD (IRB)

The Office of Human Research Ethics is responsible for ethical and regulatory oversight of research at UNC-Chapel Hill that involves human participants. The OHRE administers, supports, and guides the work of the Institutional Review Boards and all related activities. Any research involving human participants proposed by faculty, staff, or students must be reviewed and approved by an IRB before research may begin, and before related grants may be funded. OHRE and the IRBs are critical components of the coordinated Human Research Protection Program, which serves to protect the rights and welfare of human participants. All components of this program must work together to ensure institutional compliance with ethical principles and regulatory requirements. The following is a mission statement for the coordinated Human Research Protection Program:

The University of North Carolina at Chapel Hill is committed to expanding and disseminating knowledge for the benefit of the people of North Carolina and the world. An important part of that commitment to knowledge is research of the highest quality on all aspects of the health and behavior of people, and such research is only possible through the participation of humans as research participants. Human participants are partners in research and a precious resource to the university. At UNC-Chapel Hill, human participant research is a privilege, but not a right. Consistent with that philosophy, it is the mission of the UNC-Chapel Hill Human Research Protection Program to ensure that:

- a. The rights and welfare of human participants are paramount in the research process;
- b. The highest standards of ethical conduct are employed in all research involving human participants;
- c. Research investigators are properly trained in the ethical and regulatory aspects of research with human participants;
- d. Research investigators deal honestly and fairly with human participants, informing them fully of procedures to be followed, and the risks and benefits of participating in research; and
- e. Research using human participants at UNC-CH conforms to applicable local, state, and federal laws and regulations and the policies of the university.

13.3 INFORMED CONSENT PROCESS

Informed consent is a process that is initiated prior to the individual's agreeing to participate in the study and continues throughout the individual's study participation. Extensive discussion of risks and possible benefits of tACS will be provided to the participants and their families. Consent forms describing, in detail, the study intervention, device, procedures, and risks are given to the participant and written documentation of informed consent is required prior to the administration of any treatment

or assessments used in this study. All consent forms will be IRB-approved and updated with any new information as modifications are made throughout the study.

Together, the researcher and potential participants will review the clinical trial in its entirety by reviewing the consent form together in a private location. At several intervals during the consent review, the researcher will ask the participant questions that will assess the comprehension of the information in the consent. If the participant is unsure or does not know, the researcher will return to that section and more carefully explain the information. Participants must sign the informed consent document prior to any procedures taking place. If needed, the participants will have the opportunity to discuss the study with their surrogates or think about it prior to agreeing to participate. Participants may withdraw consent at any time throughout the course of the trial. A copy of the informed consent document will be given to the participants for their records. The rights and welfare of the participants will be protected by emphasizing to them that the quality of their medical care will not be adversely affected if they decline to participate in this study.

